4.3 Rationale for study design

Rationale for Primary Feasibility Endpoint:

Classification of Tumor Burden into Low-, Medium-, and High- is a validated system that aids in TLS risk stratification based on prior venetoclax clinical trials, and is in accordance with standard clinical practice and the venetoclax prescribing information. This then serves as an appropriate endpoint to evaluate the feasibility of using HDMP/R as a means to lower the risk of TLS. Using actual TLS rate would require a much larger study as the absolute rate is relatively low. There is also clinical value in decreasing the Tumor Burden to "low" prior to venetoclax administration, as less intensive monitoring is required (ie, no inpatient hospitalization).

5.0 Study Population

Subjects will undergo screening procedures within 28 days prior to initial study drug administration. Adult male and female subjects who meet the inclusion criteria and who do not meet any of the exclusion criteria will be eligible for enrollment into the study.

5.1 Inclusion Criteria

Patients must meet the following criteria for study entry:

- 1. Subjects must be age 18 or older.
- 2. Both men and women of all races and ethnic groups are eligible for this trial.
- 3. Ability to understand and willingness to sign a written informed consent.
- 4. Diagnosis: CLL or SLL, as documented in the medical record
- 5. Disease Status/ Prior Therapy:
- Must have had treatment for CLL/SLL with at least 1 line of prior therapy. (There is not requirement nor restriction for specific type of previous therapy, with the following exceptions: prior treatment with venetoclax within 6 months, prior progressive disease on venetoclax, or prior grade 3 or 4 toxicity (not including TLS) that directly lead to discontinuation of venetoclax; Prior HDMP/Rituximab is allowed unless there was no response (Stable Disease or Progressive Disease) or was within 3 months.
- Indication for CLL or SLL therapy based on international working group (iwCLL) guidelines, which include: constitutional symptoms, bulky or symptomatic lymphadenopathy, bulky or symptomatic splenomegaly, rapid doubling of the ALC (approximately 6 months or less), or Rai stage 3 or 4 disease.
- Disease burden meets criteria for Medium or High Risk for TLS, based on Absolute lymphocyte count >/= 25k/uL or any lymph node 5 cm or greater in diameter. The ALC criteria must be met during the screening period. The imaging criteria may be based on radiologic study within 30 days of Cycle 0, Day 1, if scans were done prior to consent or initiation of the screening period.
- 6. Has recovered from the toxic effects of prior therapy to their clinical baseline.
- 7. Women of child-bearing potential (not postmenopausal for at least one year or not surgically incapable of bearing children) must agree to not become pregnant for the duration of the study. Both men and women must agree to use a barrier method of contraception for the duration of the study and until 5 half-lives after the final dose of venetoclax (approximately 1 week), and at least 5 half-lives after the final dose of Rituximab.
- 8. ECOG performance status of 0-2
- 9. Adequate hematologic function: Platelet count >/= 30k/uL, hemoglobin > 7 g/dL, AND ANC > 500/uL. (Values may be lower if due to marrow infiltration by CLL).
- 10. Adequate renal function: Creatinine clearance based on 24 hr collection >/= 40 ml/min; OR Calculated Creatinine clearance (CrCl) ≥ 40 mL/min (based upon the Cockcroft-Gault Equation [CrCl = (140-age) * actual wt (in kg) * (0.85 if female) / (72 * Cr)].
- 11. Adequate hepatic function per local laboratory reference range as follows:
 - a. Aspartate transaminase (AST) and alanine transaminase (ALT) < 3.0X ULN
 - b. Bilirubin ≤1.5 x ULN (unless bilirubin rise is due to Gilbert's syndrome or of non-hepatic origin)

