- Continue allopurinol, acyclovir, and septra (or equivalent drugs, unless contraindication). Must stop fluconazole 7 days prior to first venetoclax dose.
- Week 1: Venetoclax 20 mg daily
- Week 2: Venetoclax 50 mg daily
- Week 3: Venetoclax 100 mg daily
- Week 4: Venetoclax 200 mg daily
- Week 5: Venetoclax 400 mg daily
- TLS Monitoring per venetoclax package insert.

Cycles 2-6 (28 days in duration each): Venetoclax + Rituximab

- Continue Venetoclax 400 mg PO daily (or highest tolerated dose)
- Rituximab 500 mg/m2 on day 1 of each cycle.

Cycle 7-26: Single agent Venetoclax

- Continue Venetoclax 400 mg PO daily (or highest tolerated dose)

End of Study:

- Marrow biopsy and aspirate to assess for detectable CLL (MRD)

Long-term f/up: No specific visits required. With patient consent, date of progression or next CLL therapy will be recorded.

Concomitant Medications:

- It is prohibited to take other intended CLL therapies concurrently, including purine analog, alkylating drugs, other anti-CD20 monoclonal antibody, ibrutinib, Idelalisib, etc. Corticosteroids are permitted (in cycle 0 as CLL therapy; in cycles 2-6 as anti-CD20 infusion reaction prophylaxis; and at other times for treatment of conditions other than CLL).
- Required wash out for the above is 5 half-lives or 1 month, whichever is shorter.
- GCSF, EPO, and blood transfusion are not restricted, and can be used as clinically indicated or as per clinician judgement.
- TLS prophylaxis is recommended from 3 days prior to Cycle 0 Day 1 until Cycle 2 Day 1: Allopurinol 300 mg daily (dose modified if needed; alternative uric acid lowering medication can be substituted).
- Anti-Infection Prophylaxis is recommended from 3 days prior to Cycle 0 day 1:
- Fluconazole 100 mg daily (or alternative per clinician discretion) until Cycle 1 Day 21;
- Acyclovir 400 mg BID (or alternative per clinician discretion) until Cycle 3 Day 1 (or may continue longer)
- Septra DS BID 2 days/week (or alternative per clinician discretion) until Cycle 3 Day 1 (or may continue longer)

It is prohibited to receive live viral vaccines or other investigational agents.

Version: 5 (Dec-2024)

Subject Withdrawal or Treatment Discontinuation:

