5.2 Exclusion Criteria

Patients who meet any of the following criteria will be excluded from study entry:

- 1. Subject is known to be positive for HIV. (HIV testing is not required.)
- 2. Evidence of other clinically significant uncontrolled condition(s) including, but not limited to:
 - a. Uncontrolled and/or active systemic infection (viral, bacterial or fungal)
 - b. Chronic hepatitis B virus (HBV) or hepatitis C (HCV) requiring treatment. Note: subjects with serologic evidence of prior vaccination to HBV (i.e. hepatitis B surface (HBs) antigen negative-, anti-HBs antibody positive and anti-hepatitis B core (HBc) antibody negative) or positive anti-HBc antibody from intravenous immunoglobulins (IVIG) may participate.
- 3. Treatment with any of the following within 7 days prior to the first dose of venetoclax:
 - a. Steroid therapy for anti-neoplastic intent
 - b. moderate or strong cytochrome P450 3A (CYP3A) inhibitors (see Appendix C for examples)
 - c. moderate or strong CYP3A inducers (see Appendix C for examples)
- 4. Prior CLL therapy:
 - a. Biologic agent (monoclonal antibody) within 30 days for anti-neoplastic intent.
 - b. Chemotherapy (purine analog or alkylating agent) or target small molecule agent within 14 days or 5 half-lives (whichever is shorter), or has not recovered to less than CTC grade 2 clinically significant adverse effect(s)/toxicity(s) of previous therapy.
- 5. History of severe allergic or anaphylactic reactions to monoclonal antibody therapy
- 6. Known hypersensitivity to any of the study drugs
- 7. History of other malignancy that could affect compliance with the protocol or interpretation of results (example: patients with a history of curatively treated basal or squamous cell carcinoma of the skin or in situ carcinoma of the cervix are generally eligible. Patients with a malignancy that has been treated, but not with curative intent, will also be excluded, unless the malignancy has been in remission without treatment for 2 years prior to enrollment.)
- 8. Known active bacterial, viral, fungal, mycobacterial, or other infection (excluding fungal infections of nail beds); or any major episode of infection requiring treatment with IV antibiotics or hospitalization (related to the completion of the course of antibiotics) within 4 weeks before the start of Cycle 0
- 9. Major surgery (within 4 weeks prior to the start of Cycle 0), other than for diagnosis
- 10. Women who are pregnant or lactating

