5.3 Prior and Concomitant Therapy

If a subject reports taking any over-the-counter or prescription medications, vitamins and/or herbal supplements or if administration of any medication becomes necessary beginning with the Screening visit through the end of the study, the name of the medication, dosage information including dose, route and frequency, date(s) of administration including start and end dates, and reason for use must be recorded on the appropriate case report form.

Subjects should receive full supportive care during study participation, including hematopoietic growth factors, transfusion of blood products, fluid and electrolyte replacement, and antibiotics when appropriate. Subjects who use oral contraceptives, hormone replacement therapy, or other maintenance therapy should continue their use.

Steroid therapy for anti-neoplastic intent is prescribed in Cycle 0. Aside from this, however, steroids for anti-neoplastic intent will not be allowed during or within 7 days of study treatment. Inhalational steroids for the treatment of asthma or COPD, topical steroids, replacement corticosteroid therapy for an inherited or acquired deficiency, or brief corticosteroids for rituximab infusion-reaction management or prevention are allowed.

In addition, limited corticosteroid treatment (i.e. for approximately 21 days with rapid taper) is allowed while on study for significant active autoimmune cytopenias, eg. Autoimmune hemolytic anemia (AIHA) or immune thrombocytopenia (ITP). IVIG (intravenous immune globulin) is also allowable. Eltrombopag is another treatment option for ITP.

Guidelines regarding excluded and cautionary medications are summarized in the following table.

Table 2: Excluded and Cautionary Medications (See Appendix C for Examples of the Medications)

Excluded

Anticancer therapies including chemotherapy, radiotherapy, or other investigational therapy, including targeted small molecule agents: Excluded 5 half-lives prior to first dose and throughout venetoclax administration (except the HDMP/R prescribed on study)

Biologic agents (e.g., monoclonal antibodies) for anti-neoplastic intent:

Excluded 30 days prior to first dose and throughout venetoclax administration (except the HDMP/R prescribed on study)

Excluded during ramp-up phase and Cautionary during maintenance/target dose:

Strong and Moderate CYP3A inhibitors

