- Comprehensive Metabolic Panel
- Hepatitis B and C serologies. This a standard of care assessment prior to administration of any anti-CD20 therapy and not done for the sole purpose of research). HBsAg, anti-HBs, total anti-HBc, IgM anti-HBc, HCV ab or RNA. If during screening a subject present with a positive Hepatitis B core antibody, Hepatitis B Viral DNA PCR test should be performed to rule out an active infection. If there are known results of hepatitis serologies within 6 months without at risk exposure, they do not need to be repeated.
- If female of child-bearing potential: serum pregnancy test within 14 days of initiation of therapy on trial.

Computed Tomography (CT) Scans (or Magnetic Resonance Imaging [MRI])

A CT scan must be performed within 30 days prior to study drug administration for all subjects. A CT scans should include chest, abdomen, and pelvis sequences. Contrast is preferred though can be omitted if contraindication. A contrast-enhanced MRI of chest, abdomen, and pelvis may be used for subjects in whom a CT is medically contraindicated (example: contrast allergy). Whichever method is used at Screening is preferred to be used consistently through the duration of the study for that subject.

Justification: The CT or MRI scans at baseline is a standard of care assessment prior to initiation of venetoclax in order assess tumor burden and risk for TLS, as this will guide optimal management to mitigate the risk of TLS. This test is necessary to determine if some patients may safely start venetoclax with outpatient monitoring, infusion center monitoring, or inpatient monitoring. Although this is also part of the primary endpoint assessment, it is also a needed and standard test for patient safety and in accordance with the prescribing information when venetoclax is prescribed even outside of clinical trials.

Initiation and prescription of prophylactic medication

After confirmation of eligibility, patients are prescribed allopurinol 300 mg PO daily (or dose adjusted per clinical indication such as renal failure, or alternate medication per clinician judgement), and instructed to start 3 days prior to treatment initiation.

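### The nodal baseline scan may predate the last dose of prior chemotherapy, small molecule or steroid, so shrinkage from that treatment can count as HDMP + rituximab debulking

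*Combined protocol and SAP*

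**What the plan says.** **Scan timing.** Section 5.1 item 5: "The imaging criteria may be based on radiologic study within 30 days of Cycle 0, Day 1", with scans done before consent or before screening expressly accepted. Section 6.1 repeats the window: "A CT scan must be performed within 30 days prior to study drug administration for all subjects". Table 3 (Schedule of Events) has no scan on Cycle 0 Day 1. Section 9.5 defines baseline as the last measurement before the first study dose, so the screening scan is the nodal baseline.

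**Washout before study treatment.**
- Chemotherapy and small molecules, 5.2 item 4b: "Chemotherapy (purine analog or alkylating agent) or target small molecule agent within 14 days or 5 half-lives (whichever is shorter").
- Antibodies, 5.2 item 4a: "Biologic agent (monoclonal antibody) within 30 days for anti-neoplastic intent".
- Steroids, 5.3: "steroids for anti-neoplastic intent will not be allowed during or within 7 days of study treatment".
- Steroids again, 5.2 item 3, anchored differently: "Treatment with any of the following within 7 days prior to the first dose of venetoclax".
- Synopsis, Concomitant Medications: "Required wash out for the above is 5 half-lives or 1 month, whichever is shorter". Table 2 in 5.3 gives 5 half-lives with no alternative in days.

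**Endpoint.** Sections 3.0 and 9.1 count patients who move from Medium/High to Low tumor burden. Section 4.1 describes a single-center, open-label study with no control arm. Section 9 has no rule or sensitivity analysis for recent prior therapy.

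**The concern.** The scan window is longer than two of the washouts, and no sentence ties the scan to the last prior dose. A patient could be scanned on Day -28 with a 6 cm node, receive an alkylator or a steroid until Day -15, start Cycle 0, and measure 4.5 cm on the Day 15 to 28 scan. No timing rule is broken and the patient counts as debulked. Part of the fall may belong to the earlier treatment, and the planned analysis could not show it.

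All patients have had prior therapy, and 5.1 places few limits on its type, so treatment shortly before entry is foreseeable. With 17 patients and a cut-off of 9 successes, one or two misattributed successes matter to the decision.

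**Working it through.** **1. Overlap between scan window and washout.** Longest interval in which prior treatment can fall between the scan and Cycle 0 = scan window minus washout.

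| Prior treatment | Washout | 30 days minus washout |
|---|---|---|
| Chemotherapy or small molecule, 14-day limit | 14 days | 16 days |
| Small molecule, 5 half-lives (assumed half-life 4 to 48 h) | 0.8 to 10 days | about 29 to 20 days |
| Anti-neoplastic steroid (5.3) | 7 days | 23 days |
| Monoclonal antibody | 30 days | 0 days |

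The half-lives are assumptions. The only small-molecule half-life in the documents is venetoclax's, about 26 h (5 × 26 = 130 h = 5.4 days). It serves for scale only, because venetoclax within 6 months is excluded.

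**2. The plan's own figures.** Inputs from 9.2: null rate 0.30, alternative 0.60, 10 patients in stage 1, stop at 2 or fewer successes, reject at 9 or more of 17. (One sentence in 9.2 gives the total as 20; the rest of 9.2 and the synopsis give 17, which is used here.)

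Early stopping = P(Bin(10, 0.3) ≤ 2) = 0.0282 + 0.1211 + 0.2335 = 0.3828.

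P(reject) = Σ over x = 3 to 10 of P(Bin(10, p) = x) × P(Bin(7, p) ≥ 9 − x). At p = 0.30 the terms are 0.0010 + 0.0058 + 0.0130 + 0.0130 + 0.0060 + 0.0013 + 0.0001 + 0.0000 = 0.0402. At p = 0.60 the sum is 0.8008. These reproduce the stated 0.04, 80% and 38.3%.

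**3. Adding carry-over successes (assumed number).** Let k1 patients in stage 1 and k2 in stage 2 be certain successes because of earlier treatment, the rest responding at 0.30.

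Early stopping = P(Bin(10 − k1, 0.3) ≤ 2 − k1).

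P(reject) = Σ over x ≥ 3 − k1 of P(Bin(10 − k1, 0.3) = x) × P(Bin(7 − k2, 0.3) ≥ 9 − k1 − k2 − x).

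| Carry-over successes | Early stopping | P(declare success) |
|---|---|---|
| None | 0.383 | 0.040 |
| 1, in stage 1 | 0.7⁹ + 9 × 0.3 × 0.7⁸ = 0.0404 + 0.1556 = 0.196 | 0.074 |
| 1, in stage 2 | 0.383 | 0.074 |
| 2, both in stage 1 | 0.7⁸ = 0.058 | 0.131 |
| 2, one in each stage | 0.196 | 0.131 |
| 2, both in stage 2 | 0.383 | 0.131 |

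The false-success probability hardly depends on where these patients fall. Early stopping depends on it entirely.

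**The case against.** The case that this matters little has several parts.

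- **Antibodies and re-treatment.** The 30-day antibody washout equals the scan window, so a scan before the last antibody dose is essentially ruled out. Section 5.1 also excludes venetoclax within 6 months and HDMP/rituximab within 3 months. This stands: the gap is confined to antibody-free chemotherapy, small molecules and steroids.
- **ALC.** The blood count is repeated on Cycle 0 Day 1 (6.2, Table 3) and becomes the baseline under 9.5. This largely stands, although ALC eligibility may rest on an earlier screening value. The concern is nodal.
- **Other entry criteria.** Patients need an iwCLL indication for treatment and recovery from prior toxicity. A patient whose nodes are shrinking well is less likely to qualify. This lowers the frequency; it does not exclude the case.
- **Direction.** Nodes can grow between the scan and Day 1 once therapy stops, which makes Low harder to reach. This stands.
- **Credit.** In the illustration the patient also received HDMP + rituximab before the second scan, so not all the shrinkage need be carry-over. This stands too.

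A reader might infer that the trial's result is necessarily biased in favor of HDMP + rituximab, that the real type I error is 7.4% or 13.1%, or that every prior therapy and both components of tumor burden are affected. The documents do not support these readings. They show that the rule permits carry-over; they do not show how often it occurs or which way the net bias runs.

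**Conclusion.** The gap is real and limited. As written, the plan lets the nodal baseline precede treatment with chemotherapy, a small molecule or an anti-neoplastic steroid, by up to 16 days at the 14-day limit, 23 days for steroids, and longer for short half-life agents. With no control arm and no analysis rule for recent therapy, any resulting shrinkage counts as success.

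The size rests on an assumed count. Zero, one or two carry-over successes among 17, at a true rate of 30%, give a false-success probability of 0.040, 0.074 or 0.131. The fall in early stopping from 38.3% to 19.6% or 5.8% applies only when one or two of those patients are in stage 1; it does not occur when they are all in stage 2. Zero carry-over, or net bias the other way, is also compatible with the documents. The change is worth making because it is cheap and protects the attribution on which the primary endpoint depends.

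**What to change.** Add to 5.1 item 5 and the matching synopsis entry: the scan used for eligibility and as the nodal baseline for the primary endpoint must be obtained after the last dose of prior anti-CLL therapy, including anti-neoplastic corticosteroids.

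For patients already enrolled, add to 9.7.1 a sensitivity analysis that counts as non-responders those whose baseline scan preceded their last prior dose. Section 6.1 already collects prior treatments with approximate dates; dates too imprecise to order against the scan should be queried.

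Separately, reconcile the washout statements in 5.2 item 4b, Table 2 and the synopsis, and the different anchors for steroids in 5.2 item 3 and 5.3. This review takes no position on which is right.

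Cost: eligibility wording and one extra table. An occasional patient cannot use a pre-consent scan and is scanned during screening instead, which 6.1 already provides for. An effect of prior therapy that continues after the new scan would remain.

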		clinical baseline. 7. Women of child-bearing potential (not postmenopausal for at least one year or not surgically incapable of bearing children) must agree to not become pregnant for the duration of the study. Both men and women must agree to use a barrier method of contraception for the duration of the study and until 5 half-lives after the final dose of venetoclax (approximately 1 week), and at least 5 half-lives of final dose of Rituximab. 8. ECOG performance status of 0-2 9. Adequate hematologic function: Platelet count >/= 30k/uL, hemoglobin > 7 g/dL, AND ANC > 500/uL. (Values may be lower if due to marrow infiltration by CLL). 10. Adequate renal function: creatinine clearance based on 24 hr collection >/= 40 ml/min; OR Calculated Creatinine clearance (CrCl) ≥ 40 mL/min (based upon the Cockcroft-Gault Equation [CrCl = (140-age) * actual wt (in kg) * (0.85 if female) / (72 * Cr)]. 11. Adequate hepatic function: - Aspartate transaminase (AST) and alanine transaminase (ALT) < 3.0X ULN - Bilirubin ≤1.5 x ULN (unless bilirubin rise is due to Gilbert's syndrome or of non-hepatic origin)
		Patients who meet any of the following criteria will be excluded from study entry:
		1. Subject is known to be positive for HIV. (HIV testing is not required.)
5.2	Exclusion Criteria	2. Evidence of other clinically significant uncontrolled condition(s) including, but not limited to: - Uncontrolled and/or active systemic infection (viral, bacterial or fungal) - Chronic hepatitis B virus (HBV) or hepatitis C (HCV) requiring treatment. Note: subjects with serologic evidence of prior vaccination to HBV (i.e. hepatitis B surface (HBs) antigen negative, anti-HBs antibody positive and anti-hepatitis B core (HBc) antibody negative) or positive anti-HBc antibody from intravenous immunoglobulins (IVIG) may participate.
		 3. Treatment with any of the following within 7 days prior to the first dose of venetoclax: Steroid therapy for anti-neoplastic intent moderate or strong cytochrome P450 3A (CYP3A) inhibitors (see Appendix C for examples) moderate or strong CYP3A inducers (see Appendix C for examples)
		4. Prior CLL therapy: - Biologic agent (monoclonal antibody) within 30 days for antineoplastic intent.

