6.5 Cycles 7-24: Venetoclax

Cycles 7-24 are 28 days each in duration

Patients are scheduled to be seen in clinic every 3 months

On Day 1 of Cycles 7, 10, 13, 16, 19, and 22, the following are completed:

- History and physical examination including vital signs.
- Current medications will be recorded in the subject's medical record.
- Laboratory examinations: CBC w/differential, comprehensive metabolic panel, phosphorous, uric acid
- Dispensing of Venetoclax 400 mg PO dose (or highest tolerated dose), 90 day supply.

In addition, on Day 1 of Cycle 10

- CT or MRI of thorax, abdomen, and pelvis. Areas that did not have enlarged lymph nodes (greater than 1.5 cm in long-axis diameter on the prior scan) or spleen may be skipped for this radiographic reassessment.
- Marrow biopsy and aspirate if clinical examination is consistent with a complete remission (ie, absolute lymphocyte count less than 4k/uL) and if clinically indicated to determine subsequent therapy (eg: stopping therapy if undetectable minimal residual disease).

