6.7 Long-term follow-up

No long-term follow-up visits are scheduled or required per study.

With patient consent, date of progression or next CLL therapy will be recorded based on chart review if data are available, or phone call no more than every 6 months.

6.8 Subject Withdrawal or Treatment Discontinuation:

Patients who meet or develop the following criteria should be discontinued from the study

- Active HBV infection or hepatitis. Patients who are carriers of hepatitis B at the time of discontinuation from study treatment will continue to be followed for clinical and laboratory signs of active HBV infection and for signs of hepatitis.
- Severe or life-threatening anaphylaxis or hypersensitivity reaction to rituximab. Patients that discontinue rituximab for that reason can continue to receive HDMP and venetoclax if clinically indicated.
- Patients who meet the following criteria should discontinue HDMP: Grade 4 psychosis; Active HBV infection or hepatitis as above. HDMP doses can be delayed for acute infection or as clinically indicated.
- Inability of patient to comply with study requirements
- Determination by the investigator that it is no longer safe for the patient to continue therapy

With the exception of following HBV, patients who withdraw from all study therapy do not have required follow-up visits and can enter long-term follow-up (6.7). With patient consent, date of progression or next CLL therapy will be recorded.

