A positive response to tetanus toxoid vaccine (a T-cell dependent antigen with existing immunity) was similar in patients treated with RITUXAN plus MTX compared to patients on MTX alone (39% vs. 42%). The proportion of patients maintaining a positive Candida skin test (to evaluate delayed type hypersensitivity) was also similar (77% of patients on RITUXAN plus MTX vs. 70% of patients on MTX alone).

Most patients in the RITUXAN-treated group had B-cell counts below the lower limit of normal at the time of immunization. The clinical implications of these findings are not known.

Embryo-Fetal Toxicity

Based on human data, RITUXAN can cause fetal harm due to B-cell lymphocytopenia in infants exposed to rituximab in-utero. Advise pregnant women of the risk to a fetus. Females of childbearing potential should use effective contraception while receiving RITUXAN and for 12 months following the last dose of RITUXAN.

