	2 nd and subsequent occurrence	Interrupt venetoclax. Consider using G-CSF as clinically indicated. Follow dose reduction guidelines in Table 5 when resuming treatment with venetoclax after resolution. Additional dose reductions may occur at the discretion of the physician.	

Consider discontinuing venetoclax for subjects who require dose reductions to less than 100 mg for more than 2 weeks.

Management of Neutropenia

Based on clinical observations with the 1st generation Bcl-2 inhibitor, navitoclax and in vitro colony-forming assays to assess Bcl-2-selective inhibitor effects on granulocyte precursors, it is possible that subjects treated with venetoclax might experience neutropenia. Subjects with a history of neutropenia, who have received multiple prior therapies and/or have significant bone marrow involvement, may be at particular high risk. If determined to be clinically indicated by the treating physician in compliance with ASCO guidelines, G-CSF may be administered during dosing of venetoclax. The use of G-CSF support is strongly recommended for subjects with Grade 4 neutropenia (ANC < $500/\mu$ L). If the subject presents with febrile neutropenia or Grade 4 neutropenia for more than one week despite the use of optimal G-CSF support, venetoclax dosing should be interrupted until ANC recovery to > $500/\mu$ L. Venetoclax may then be re-initiated at a

Adverse reactions were graded using NCI CTCAE version 4.03.

b. Clinical TLS was defined as laboratory TLS with clinical consequences such as acute renal failure, cardiac arrhythmias, or sudden death and/or seizures.

lower dose as defined in the following table. Subjects not responding to G-CSF despite venetoclax interruption should undergo further evaluation to determine the etiology of the neutropenia.

Table 5. Dose Modification for Toxicity during Venetoclax Treatment.

Venetoclax Dose	Reduced Dose	
400 mg	300 mg	
300 mg	200 mg	
200 mg	100 mg	
100 mg	50 mg	
50 mg	Re-challenge at 20 mg ^a	

a. Subjects who do not tolerate 20 mg will discontinue venetoclax, but may remain on study to assess for progression.

Management of Lymphopenia

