9.2 Sample size justification

Seventeen patients are enrolled to evaluate the primary endpoint. A success rate of 60% of patients adequately debulking (defined as having low Tumor Burden at the end of cycle 0) will be considered compelling, establishing the feasibility of this approach, and support further studies. A success rate of 30% would be not compelling for further studies. With 17 patients, the study is adequately powered to evaluate this. A Simon's two-stage minimax design is utilized, with stopping for futility if an insufficient number of patients are debulked by HDMP/Rituximab. This design will have 80% power to reject the null hypothesis at 4% significance level and conclude that the true debulking rate at cycle 0 is above 30%, if the observed rate is ≥60%. Note that if patients are still meeting med/high tumor burden, they may repeat cycle 0 once more.

The null hypothesis that the true debulking rate is 30% at Cycle 0 will be tested against a one-side alternative. In the first stage, 10 patients will be accrued. The study enrollment will be put on hold for interim analysis until the response results for Stage 1 patients are known. If there are 2 or fewer responses (patients achieving low Tumor Burden) in these 10 patients, the study will be stopped. Otherwise, 7 additional patients will be accrual for a total of 20. The null hypothesis will be rejected if 9 or more responses are observed in 17 patients.

Early stopping probability: Under this design, if the null hypothesis is true, the probability of stopping the trial early will be 38.3%. The sample size calculation was done using PASS version 14.0.3 (released September 22, 2015). Sample size calculation did not incorporate the safety endpoint. Statistics for safety outcomes will be presented descriptively.

Accrual and study duration

We expect to accrue 1-2 patients every month. All patients will be accrued within 12-24 months. Patients will be followed for 24 months. The total duration of this study will be about 36 months.

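### Criterion 7 sets post-rituximab contraception at 5 half-lives, which may fall short of the 12 months in 7.2.3 for women of childbearing potential who leave the study early

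*Combined protocol and SAP*

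**What the plan says.** Criterion 7 in section 5.1 has three terms: barrier contraception while the study lasts, 5 half-lives after the last venetoclax dose (glossed there as roughly a week), and "at least 5 half-lives after the final dose of Rituximab". The synopsis has the same rule, worded "at least 5 half-lives of final dose of Rituximab". Neither place converts the rituximab term to days or months, and no rituximab half-life is given elsewhere.

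The embryo-fetal toxicity paragraph of 7.2.3 warns of fetal harm and says: "Females of childbearing potential should use effective contraception while receiving RITUXAN and for 12 months following the last dose of RITUXAN". Section 7.2 introduces 7.2.1 to 7.2.4 as background information on the product.

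Section 6.8 opens its list with "Patients who meet or develop the following criteria should be discontinued from the study"; one entry is "Inability of patient to comply with study requirements". Apart from hepatitis B follow-up, it requires no visits after withdrawal from all study therapy. Such patients may move into the long-term follow-up of 6.7, which records only progression or next CLL therapy.

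No text reconciles the 5 half-lives with the 12 months.

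**The concern.** Criterion 7 is what a woman agrees to at entry. If its rituximab term is shorter than the period in 7.2.3, she can keep her commitment in full and still become pregnant inside the window that the same protocol associates with fetal harm. She also cannot work out from the protocol when that term ends.

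After early exit there is little else to rely on. The text lists a pregnancy test only at screening (6.1), and 6.8 requires no further visits beyond hepatitis B follow-up. The matter is one of participant safety and clear commitments; it does not touch the inference.

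**Working it through.** **Inputs.** Venetoclax half-life about 26 hours (2.2.3.1). Last planned rituximab dose on Cycle 6 Day 1 (7.2.2). Cycles of 28 days after Cycle 1 (6.4). End of study at Cycle 24 Day 28, plus or minus 2 weeks (6.6). Period in 7.2.3: 12 months, taken as 365 days. Rituximab half-life *h*: not in the documents. I assume 10 to 40 days and extend the table to 80 to show where the conclusion turns.

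**1. The plan's own conversion.** Venetoclax: 5 × 26 h = 130 h = 5.4 days. This fits the stated week, so the half-life rule is being applied as one would expect.

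**2. Break-even for rituximab.** 5*h* < 365 when *h* < 365/5 = 73 days.

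| Assumed *h* (days) | 5*h* (days) | Short of 365 by |
|---|---|---|
| 10 | 50 | 315 |
| 20 | 100 | 265 |
| 30 | 150 | 215 |
| 40 | 200 | 165 |
| 60 | 300 | 65 |
| 73 | 365 | 0 |
| 80 | 400 | no gap |

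**3. Completers.** Cycle 6 Day 1 to Cycle 24 Day 28 is 19 × 28 − 1 = 531 days, or 517 to 545 with the window. All exceed 365, so the study-duration term alone covers these women. The synopsis schedules venetoclax through Cycle 26, which would lengthen this to 21 × 28 − 1 = 587 days.

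**4. Early leavers.** For a woman who leaves the study *d* days after her last rituximab dose, criterion 7 runs for the larger of 5*h* and *d* (plus 5.4 days if she was on venetoclax until exit). Two nominal examples:

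- Exit at the end of Cycle 0, last dose on Day 4, no venetoclax: *d* = 28 − 4 = 24. The larger of 50–200 and 24 is 50–200 days.
- Exit at the end of Cycle 6, last dose on Day 1: *d* = 27, and 27 + 5.4 = 32.4. The larger of 50–200 and 32.4 is again 50–200 days.

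In both, the half-life term governs, and the shortfall of 165 to 315 days simply restates the assumed *h*. The gap narrows as exit comes later. With the last dose on Cycle 6 Day 1, 365 days is reached at Cycle 19 Day 2 (13 × 28 = 364 days to Cycle 19 Day 1).

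**5. Who can leave early.** The wording of 6.8 quoted above takes certain patients out of the study, and so ends the study-duration term if read literally. A stop after the Cycle 10 marrow ("stopping therapy if undetectable minimal residual disease" in 6.5) ends treatment but not necessarily the study.

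**The case against.** The strongest reply is that nothing conflicts. Criterion 7 sets a floor, 7.2.3 is background product text worded as advice, and a woman who follows 7.2.3 complies with both. That stands: a reader might infer two contradictory binding rules, and the documents do not support that. But a floor that permits 12 months does not ask for it. The protocol does carry other 7.2.3 advice into its operating sections: hepatitis B precautions reappear as screening in 6.1 and as follow-up after discontinuation in 6.8. The embryo-fetal period was not carried over.

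A second reply is that 6.8 does not show that anyone is truly off study. Its list also includes patients who stop only rituximab or only HDMP, so its opening line is used loosely, and withdrawn patients may enter long-term follow-up. The Table 5 footnote in 7.3.4 says that subjects who cannot tolerate 20 mg "will discontinue venetoclax, but may remain on study to assess for progression", and 9.2 says "Patients will be followed for 24 months". If such patients still count as on study, or if study duration means planned duration, much or all of the gap closes. This also stands in part. One might infer that every patient discontinued under 6.8, or every woman who stops after the Cycle 10 marrow, is left uncovered. The text does not settle the first, and the second is less certain still.

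Third, the size depends on a half-life that the documents do not supply. Correct: only the 73-day condition follows from the text.

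Finally, the consent pages were not available for this review and may already state 12 months. No error there is alleged.

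**Conclusion.** The point holds, as a minor one. Criterion 7 commits women of childbearing potential to a shorter post-rituximab period than 7.2.3 advises if the half-life is below 73 days. On the assumed 10 to 40 days, the term is 50 to 200 days against 365.

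It matters only for women who leave the study within 12 months of their last rituximab dose. A reader might infer that all women enrolled are under-protected; the 531 days from last planned dose to end of study rule that out for completers. Nor are men affected, because the 12 months in 7.2.3 is addressed to females.

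Discontinuation under 6.8 is the most direct route, subject to the ambiguity about who remains on study. The documents give no expected number of women of childbearing potential, so the number affected among 17 patients may be zero. Endpoints, alpha and power are untouched.

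**What to change.** In criterion 7, in both 5.1 and the synopsis, replace the rituximab term for women of childbearing potential with *for at least 12 months after the final dose of rituximab*. Leave the term for men as it is. Repeat the 12-month period in 6.8 for women discontinued early, so that it applies whether or not they count as on study, and check that the consent wording agrees.

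The cost is a wording amendment and a longer contraception commitment for a few women, which 7.2.3 already advises. The sample size and analysis stay as they are.
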